4. LIST OF ABBREVIATIONS

The following abbreviations are used in this study protocol:

Abbreviation or specialist term	Explanation
AE	adverse event
ANC	absolute neutrophil count
CFR	Code of Federal Regulations
CTCAE	Common Terminology Criteria for Adverse Events
COVID-19	Coronavirus Disease 2019 caused by the SARS-CoV-2 virus
DSMB	Data and Safety Monitoring Board
eCRF	electronic case report form
EDC	electronic data capture
FDA	Food and Drug Administration
FEV1	forced expiratory volume in 1 second
FVC	Forced Vital Capacity
GCP	Good Clinical Practice
ICH	International Conference on Harmonisation of Technical Requirements for Registration of Pharmaceuticals for Human Use
IRB	Institutional Review Board
MERS-CoV	Coronavirus causing Middle East Respiratory Syndrome
ODN	ODN M362
OHRP	Office for Human Research Protections
Pam2	Pam2CSK4
PUL-042	drug product consisting of a 4:1 molar ratio of Pam2:ODN; Inhalation Solution
Pulmotect	Pulmotect, Inc.
SAE	serious adverse event
SAP	statistical analysis plan
SARS-CoV	Coronavirus causing Severe Acute Respiratory Syndrome
SARS-CoV-2	Coronavirus causing COVID-19
SWFI	sterile water for injection
TLR	Toll-like receptor
USP	United States Pharmacopeia
WHO	World Health Organization

5. BACKGROUND

This protocol is being conducted under a COVID-19 specific IND filed with the Division of Pulmonary, Allergy and Critical Care of the FDA and is intended to provide preliminary data on the efficacy and safety of PUL-042 in subjects positive for SARS-CoV-2 infection. Evaluation of these data will determine the feasibility of advancing to Phase 3 clinical development to pursue an NDA filing and the potential for Emergency Use Authorization.

This section includes a brief summary of the rationale for clinical investigation of PUL-042 and a summary of the nonclinical data available on PUL-042. More detailed information can be found in the Investigator's Brochure.

[figure not shown]
5.1. Introduction

Respiratory infection can be caused by a variety of pathogenic organisms including bacteria, fungi, and viruses and is one of the leading causes of death worldwide¹. Even in developed countries, respiratory infection continues to be the leading cause of death from infection and a serious complication for patients being treated for other diseases. The threat of respiratory infections is elevated when there is a decreased level of host resistance such as in immunosuppressed individuals and when there is an increased level of pathogen exposure such as in the case of bioterror attacks and biowarfare or epidemics and pandemics such as the current COVID-19 pandemic.

Pulmotect, Inc. (Pulmotect) has developed a novel therapeutic to stimulate innate immunity in the lungs that may provide protection against lower respiratory tract infection. The technology platform is a direct result of basic research conducted by Pulmotect's founders on the mechanisms of microbial resistance in the lung epithelium^{2,3,4,5,6}. PUL-042 is a combination of two synthetic molecules, a lipopeptide (Pam2CSK4 acetate [Pam2]) and a phosphorothioate oligodeoxynucleotide (ODN M362 sodium [ODN]) that act synergistically as agonists of Toll-like receptors (TLR)2/6 and TLR9, respectively. The response is primarily localized and specific to the site of administration. In animal studies, inhalation treatment with PUL-042 results in increased survival rates after respiratory exposure to a broad spectrum of pathogens including Gram-positive and Gram-negative bacteria (including three Class A bioterror agents), the fungus *Aspergillus fumigatus*, and viral pathogens.

[figure not shown]
The activity of PUL-042 before and after a pathogen challenge has been evaluated in animal models against a range of viruses as a single agent⁷ and in combination with existing anti-viral drugs, including oseltamivir against influenza H3N2 for successful treatment at more advanced stages of infection⁸.

Figure 1: PUL-042 treatment has been demonstrated to protect mice against Influenza A/HK/8/68 (H3N2)

Antiviral activity has also been demonstrated against coronavirus strains. In unpublished experiments conducted at the University of Texas Medical Branch at Galveston a single inhaled dose of PUL-042 was shown to protect mice from SARS-CoV, and significantly reduced the amount of virus in the lungs after infection with MERS-CoV virus (Figure 2). The antiviral activity of PUL-042 therefore has the potential for the prevention of infection with the SARS-CoV-2 virus.

[figure not shown]
Figure 2: Pretreatment with PUL-042 has been demonstrated to protect mice against SARS-CoV and MERS-CoV

5.2. Chemical Name and Structure

The investigational product, PUL-042 Inhalation Solution, is a combination of Pam2 and ODN. Pam2 is a synthetic 6-amino acid lipopeptide as an acetate salt, and ODN is a synthetic 25-base, single-stranded oligonucleotide that contains unmethylated CpG dinucleotides with a phosphorothioate backbone as a sodium salt. The structure of Pam2 and nucleotide sequence of ODN are shown in Figure 3.

Figure 3 Structure and Nucleotide Sequence of PUL-042 Components Pam2 and ODN
Pam2

C = carbon; H = hydrogen; O = oxygen; S = sulfur; Ser = serine, Lys = lysine; MW = molecular weight

ODN

5'-TCG TCG TCG TTC GAA CGA CGT TGA T-3' M.W.: 8,049.5
(single-stranded, nuclease-resistant phosphorothioate oligodeoxynucleotides)

5.3. Nonclinical Studies

The nonclinical pharmacology, pharmacokinetics, and toxicology of PUL-042 are described in detail in the Investigator's Brochure.

5.4. Clinical Studies

The initial phase 1 study of PUL-042 Inhalation Solution (PUL-042-001) "A Randomized, Double-Blind, Placebo-Controlled, Ascending Dose Study to Assess the Safety, Tolerability, Pharmacokinetics and Pharmacodynamics of PUL-042 Inhalation Solution in Healthy Subjects" has been completed. Subjects were administered a single dose of PUL-042 Inhalation Solution by nebulization. A total of 4 mL of a solution of PUL-042 at increasing concentrations was administered using sterile water for injection (SWFI) as the diluent.

Review of the data from the PUL-042-001 study indicated that there was a potential pharmacodynamic effect indicated by a rise in the absolute neutrophil count (ANC) as measured at 4 hours post dose in subjects treated with PUL-042 Inhalation Solution compared to placebo. The ANC was at or near baseline levels when measured again at 24 hours post dose. All values were within the normal range at the 24-hour time point. The neutrophil response was confirmed in sheep and mice, and furthermore was shown to be dose dependent in mice. The time course of that response has been further explored in subjects in the study PUL-042-003 "A Randomized, Open-label, Crossover Study to Assess the Safety, Tolerability and Pharmacodynamics of PUL-042 Inhalation Solution in Healthy Subjects and the Effect of Pretreatment with Cromolyn Sodium or Albuterol Sulfate".

A similar potential pharmacodynamic effect was seen in the spirometry data (specifically the forced expiratory volume in 1 second [FEV1]) from PUL-042-001, likely due to the effect of PUL-042 on the bronchial airways. A dose-dependent decrease in FEV1 was seen with a nadir at approximately 30 minutes post-dose in subjects treated with PUL-042 Inhalation Solution. There was no comparable decline observed with placebo. These measurements were largely within the 12% change from baseline accepted as normal variability. This was followed by a recovery to near baseline levels at 24 hours post dose. Over the course of 7 days, the mean FEV1 was within 0-5% of the baseline value, with the subjects who received higher doses of PUL-042 showing a larger mean decrease in FEV1. None of the decreases in FEV1 were accompanied by signs of respiratory distress or a drop in oxygen saturation. None of the FEV1 results in the PUL-042 inhalation treated groups were statistically different from placebo after the 30-minute time point. The MTD delivered as a single dose was established as 40.6 µg Pam2 : 59.5 µg ODN in PUL-042-001.

A second phase 1 study (PUL-042-003) has been completed. PUL-042-003 was a randomized, open-label, cross-over study to determine the safety and tolerability of PUL-042 Inhalation Solution and to explore the effect of pretreatment with either cromolyn sodium or albuterol sulfate. The primary objective of this study was to determine the safety and tolerability in healthy normal subjects of single or repeated doses of PUL-042 in SWFI. Exploratory objectives include determining whether ANC was an indicator of biological activity and to determine 1) the duration of local biological activity in the bronchial airways by serial FEV1 measurements, 2) whether the administration of cromolyn sodium prior to the administration of PUL-042 had an effect on the FEV1 response, and 3) whether the administration of albuterol prior to the administration of PUL-042 had an effect on the FEV1 response.

In protocol PUL-042-003, the first cohort of 8 subjects (cohort 1) received a dose of 20.3 µg Pam2 : 29.8 µg ODN (1/2 the single-dose MTD of PUL-042) with or without pretreatment with cromolyn sodium (4 each). Subjects were then crossed over to the alternative treatment after a 2-week follow-up period and an additional 2-week washout period.

A similar design was used for the second cohort (8 subjects) with PUL-042 +/- albuterol sulfate. The second cohort of subjects received a total dose of 40.6 µg Pam2 : 59.5 µg ODN as two doses over 3 days (1 dose on Day 1 and 1 dose on Day 3) and a total dose of 81.2 µg Pam2 : 119 µg ODN as four doses over 32 days (1 dose each on Day 1, Day 3, Day 29 and Day 32).

Results from PUL-042-003 showed no clinically significant abnormalities or changes from baseline for vital signs, electrocardiography, pulse oximetry, physical examination, or safety laboratory assessments.

In general, FEV1 results were consistent with those seen in PUL-042-001 with an early onset decrease in FEV1 in some subjects that spontaneously reversed to near baseline levels over several minutes to hours. In the PUL-042-001 study, a small decrease in average FEV1 was also observed 7 days post-treatment (the last observation in that study) compared to the pre-dose baseline. A similar pattern was observed through 7 days post-treatment in PUL-042-003. Observations at later time points showed sporadic decreases in FEV1 values, but longer-term follow-up measurements of FEV1 gave results comparable to the initial pre-dose baseline values. As in study PUL-042-001, none of the decreases in FEV1 were accompanied by signs of respiratory distress or a drop in oxygen saturation. Pre-treatment with cromolyn sodium or albuterol sulfate had no significant effect on the short lasting FEV1 decreases observed following administration of PUL-042.

Currently there is an ongoing Phase 2 study, PUL-042-402 (A Phase 2, Single-Center, Double-Blind, Placebo-Controlled Study of PUL-042 Inhalation Solution in Rhinovirus-induced Symptoms in Current Smokers with GOLD Stage 0 COPD), that is evaluating the effects of PUL-042 on peak lower respiratory symptoms and safety in subjects with an experimentally induced rhinovirus infection with laboratory human rhinovirus strain HRV A16.

Subjects are dosed with PUL-042 (20.3 µg Pam2 : 29.8 µg ODN [50 µg PUL-042]) or placebo 24 hours prior to viral inoculation and again 48 hours post inoculation. The subjects are then followed for 6 weeks. To date, 19 of the planned 24 subjects have completed the study and data from 18 subjects reviewed by the Data Safety Monitoring Board (DSMB). The DSMB approved enrolling 6 additional subjects based on the data from these subjects. The study has been suspended due to the COVID-19 pandemic but, is anticipated to re-start in Q4 2020. The study remains blinded to treatment related efficacy and safety. There have been no Serious Adverse Events reported and no apparent safety concerns with PUL-042 administration following a respiratory viral infection.

5.5. Dosing

The dose selected is based on the results of PUL-042-001, a single ascending dose study to determine the maximum tolerated dose of PUL-042 in healthy volunteers, PUL-042-003, an open-label crossover study to investigate the effects of pretreatment with cromolyn sodium or albuterol sulfate on the safety, tolerability, and pharmacodynamics of PUL-042 administered to healthy volunteers and PUL-042-402 an ongoing double-blind study of PUL-042 in a COPD rhinovirus challenge model.

Based on the results of these studies, the dose level of PUL-042 Inhalation Solution in the current study will be 20.3 µg Pam2 : 29.8 µg ODN/mL (50 µg PUL-042 [this is the same dose level currently used in the ongoing viral challenge study]). A total of up to 3 doses will be administered over a 1-week period for a total dose of 60.9 µg Pam2 : 89.4 µg ODN.

Doses of PUL-042 or placebo will be prepared by an unblinded pharmacist and administered to the subject within 4 hours of preparation. Further details will be supplied in a Pharmacy Manual.

Doses will be administered via nebulization to deliver 4 mL using a PARI Sprint nebulizer equipped with a filter valve to prevent aerosol generation. The nebulizer will be operated until all drug is delivered. Each nebulizer will be disposed using appropriate precautions after a single use. A nose clip will be used during the nebulization procedure.

Despite the use of the above nebulization equipment health care professionals should wear appropriate personal protective equipment and observe the procedure from a distance of at least six feet or preferably from another room until after nebulization has been completed.

6. STUDY OBJECTIVES

6.1. Primary Objective

To determine the efficacy of PUL-042 Inhalation Solution in decreasing the severity of COVID-19 in subjects: 1) who have documented SARS-CoV-2 infection, and 2) if receiving oxygen, should have pulse oximetry $\geq 93\%$ on 3 liters per minute of oxygen or less delivered by nasal prongs (Ordinal Scale for Clinical Improvement 4 or less) at the time of enrollment.

The primary endpoint is the difference in the proportion of patients with clinically meaningful worsening of COVID-19 within 28 days from the start of experimental therapy, as indicated by an increase of at least 2 points on the Ordinal Scale for Clinical Improvement.

6.2. Secondary Objectives

To determine the difference in the proportion of COVID-19 patients with clinically meaningful worsening of COVID-19 within 14 days from the start of experimental therapy, as indicated by an increase of at least 2 points on the Ordinal Scale for Clinical Improvement.

To assess the progression of COVID-19 severity during the study as measured by the Ordinal Scale for Clinical Improvement

To assess the progression of COVID-19 severity during the study as measured by the SARS-CoV-2 Symptom Score

To determine SARS-CoV-2 positivity 28 days from the start experimental therapy

To determine mortality rate at 28 days after start of PUL-042 therapy

To assess the requirement for ICU admission within 28 days from the start of experimental therapy

To assess the requirement for mechanical ventilation within 28 days from the start of experimental therapy

To determine the tolerability of PUL-042 Inhalation Solution in this population

7. INVESTIGATIONAL PLAN

7.1. Overall Study Design

This will be a double-blind trial. A total of 100 subjects randomized 1:1 (PUL-042 Inhalation Solution: placebo) will be enrolled in the trial.

Doses will be administered via nebulization with a PARI Sprint nebulizer. All subjects will receive 3 doses of PUL-042 Inhalation Solution or placebo over 1 week (Days 1, 3, and 6).

Note: There is no Day 0 in this study.

An overview of the study design is presented in [Figure 4](#).

Figure 4: Study Design

PUL-042-502 STUDY OVERVIEW

7.2. Subject Selection

7.2.1. Inclusion Criteria

Subjects aged 18 years or older must fulfill all of the following inclusion criteria to be eligible for the study:

1. Subjects must have a positive test for SARS-CoV-2.
2. COVID-19 signs and symptoms such as (fever, cough, shortness of breath or fatigue) with onset within the 7 days prior to Screening and/or within 9 days of the first dose administered on Day 1
3. Subjects should be Ordinal Scale for Clinical Improvement score of 4 or less
4. Subjects receiving oxygen should have pulse oximetry $\geq 93\%$ on 3 liters per minute of oxygen or less delivered by nasal prongs
5. Subjects can be receiving standard of care (SOC) for COVID-19, this includes marketed therapies or therapies with Emergency Use Authorization (EUA) for COVID-19 treatment.
6. Subject's spirometry (FEV₁ and forced vital capacity [FVC]) must be $\geq 70\%$ of predicted value.

7. If female, the subject must be surgically sterile or \geq 1 year postmenopausal. If of child-bearing potential (including being $<$ 1 years postmenopausal) and, if participating in sexual activity that may lead to pregnancy, the subject agrees to use an effective dual method of birth control (acceptable methods include intrauterine device, spermicide, barrier, male partner surgical sterilization, and hormonal contraception) during the study and through 30 days after completion of the study.
8. If female, must not be pregnant, plan to become pregnant, or nurse a child during the study and through 30 days after completion of the study. A pregnancy test must be negative at the Screening Visit, prior to dosing on Day 1.
9. If male, must be surgically sterile or, if not surgically sterile and if participating in sexual activities that may lead to pregnancy, be willing to practice two effective methods of birth control (acceptable methods include barrier, spermicide, or female partner surgical sterilization) during the study and through 30 days after completion of the study.
10. Must have the ability to understand and give informed consent.

7.2.2. Exclusion Criteria

Subjects will be excluded if they fulfill any of the following exclusion criteria:

1. No documented infection with SARS-CoV-2.
2. Patients who are in respiratory distress or require high flow oxygen, non-invasive ventilation or mechanical ventilation (Ordinal Scale for Clinical Improvement $>$ 4) or with pulse oximetry less than 93% on oxygen with a flow rate of 3 liters per minute or less by nasal prongs at the time of screening.
3. Known history of chronic pulmonary disease (e.g., asthma [including atopic asthma, exercise-induced asthma, or asthma triggered by respiratory infection], chronic pulmonary disease, pulmonary fibrosis, COPD), pulmonary hypertension, or heart failure.
4. Exposure to any investigational therapy (defined as any agent not currently marketed or without EUA) at the time of or within 30 days prior to the Screening Visit.
5. Any condition which, in the opinion of the Principal Investigator, would prevent full participation in this trial or would interfere with the evaluation of the trial endpoints.

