7.9. Study Day -2 to Day 1 (Screening)

The following assessments will be conducted prior to performing any study-specific procedures:

- Informed consent: The subject will sign an informed consent form approved by the governing Institutional Review Board (IRB) or Ethics Committee.

Once the informed consent is obtained, the following will be conducted as part of Screening to document subject eligibility for the study.

- Medical history (including documentation of SARS-CoV-2 infection and date of onset of symptoms of SARS-CoV-2 infection)
- Physical examination (including height and weight)
- Serum pregnancy test or urine test (if urine test is positive, a serum test must be conducted)
- Vital signs
- Pulse oximetry
- Spirometry
- Nasopharyngeal or oropharyngeal sample for SARS-CoV-2 testing if a positive test for SARS-CoV-2 has not been documented
- SARS-CoV-2 infection symptom score
- Ordinal Scale for Clinical Improvement assessment
- Concomitant medication assessment
- Randomization to study treatment
- Adverse event (AE) assessment (AE collection starts at the time the time of randomization to study treatment and is continuous throughout the study until 28 days after receiving study drug)

7.10. Study Day 1

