7.10.1. Day 1 (Pre-dose)

Assessments conducted during Screening do not have to be repeated if done on Day 1.

The following should be obtained prior to dosing.

- Physical examination
- Vital signs
- Spirometry
- SARS- CoV-2 infection symptom score
- Ordinal Scale for Clinical Improvement assessment
- Adverse event assessment
- Concomitant medication assessment

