4.2 Analysis Sets

The following two analysis sets will be defined for this study:

Intent to Treat (ITT) Set

The ITT set is defined as all randomized subjects who receive at least one dose of experimental treatment (i.e., PUL-042 or Placebo). The primary analysis of all efficacy endpoints will be carried out using the ITT set based on the randomized treatment.

Safety (SAF) Set

The SAF set is also defined as all randomized subjects who receive at least one dose of experimental treatment (i.e., PUL-042 or Placebo), but subjects are categorized based on the treatment actually received rather than as randomized. All safety and tolerability analyses will be carried out using the SAF set. If, as expected, the Safety analysis set is redundant (i.e., is identical to the ITT analysis set), the ITT set will be used for the assessments of safety and tolerability.

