4.6 Data Derivations and Transformations

The following derivations will be used in this study:

Study Day (Note: There is no day 0 in this study):

- Date of assessment – date of 1st Study Drug administration + 1 for assessments done on or after date of 1st Study Drug administration
- Date of assessment – date of 1st Study Drug administration for assessments done before date of 1st Study Drug administration

Baseline Observation: the last non-missing value prior to 1st Study Drug administration.

Duration:

- Duration in days = end date – start date + 1

- Duration in minutes = end time in minutes – start time in minutes

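### Randomization can precede dosing by up to 2 days with no stated Day 1 eligibility re-check, so a subject can be dosed at baseline score 5, from which an intubation scored 6 is not a primary event

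*Protocol*

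**What the plan says.** **Timing of randomization.** Protocol 7.9 lists "Randomization to study treatment" among the Screening activities. Table 1 and SAP Appendix A mark it in the Screening column, Day -2 to Day 1. Inclusion 2 allows for the gap, with symptom onset "within the 7 days prior to Screening and/or within 9 days of the first dose administered on Day 1".

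**Timing of eligibility.** Exclusion 2, which names scores above 4, is judged at "3 liters per minute or less by nasal prongs at the time of screening". Inclusion 3 ("Subjects should be Ordinal Scale for Clinical Improvement score of 4 or less") has no time point, nor do inclusion 4 (oximetry on oxygen) and inclusion 6 (FEV1 and FVC at least 70% "of predicted value"). Section 7.9 and footnote e of Table 1 describe Screening as the visit that documents eligibility. The primary objective (Protocol 6.1 and 13.3, SAP 2.1.1) ties the limit of 4 to enrollment, which neither document defines.

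**Day 1.** Protocol 7.10.1 collects the Ordinal Scale and spirometry before dosing and adds: "Assessments conducted during Screening do not have to be repeated if done on Day 1". It attaches no threshold or consequence to the values. The pre-dose hold-or-stop guideline in 7.11.1 is written for Days 3 and 6. The discontinuation rule in 7.10.2 stands under the post-dose guidelines, concerns further dosing, and does not name score 5. Pulse oximetry is scheduled at Screening only.

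**Analysis.** SAP 4.6: "Baseline Observation: the last non-missing value prior to 1st Study Drug administration". SAP 6.1 counts a rise of 2 or more points from baseline as worsening. SAP 4.2: "The ITT set is defined as all randomized subjects who receive at least one dose of experimental treatment".

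**The concern.** The primary objective concerns subjects at score 4 or less. Under that ceiling, intubation (6) is always a rise of at least 2 points, so the endpoint captures it from every permitted baseline. That property is lost if baseline is measured after the point at which the ceiling is checked, and the subject has moved to 5 in between.

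A subject who worsens between Screening and Day 1 can go one of two ways:

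- **Dosed.** The subject enters the primary analysis at a baseline outside the stated population. Intubation at score 6 is a non-event on the primary endpoint but counts as mechanical ventilation under SAP 6.2. The two endpoints then disagree about the same clinical course.
- **Not dosed.** The subject has been randomized but is not in the ITT set, so the analysed set is no longer the randomized set.

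Other provisions do not clearly catch either case. SAP 6.3 specifies a sensitivity analysis for symptom onset, but none for a baseline above 4 or for all randomized subjects. The major-deviation category for eligibility violations (Protocol 14.5) need not apply to someone who satisfied exclusion 2 at Screening.

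**Working it through.** The plan gives no event rate, effect size or power for this endpoint, so there is no stated figure to reproduce. The check is one of timing and scale arithmetic.

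**1. Length of the gap.** By SAP 4.6, study day before first dose = assessment date − first-dose date. Day -2 is therefore 2 calendar days before Day 1. Inclusion 2 agrees: 7 days before Screening + 2 = 9 days before first dose. The gap is 0 when Screening is on Day 1.

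**2. Which scores count from each baseline.** An event requires score − baseline ≥ 2.

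| Baseline | Score needed | 6 (intubation) | 7 (organ support) | 8 (death) |
|---|---|---|---|---|
| 3 | 5 | +3, event | +4, event | +5, event |
| 4 | 6 | +2, event | +3, event | +4, event |
| 5 | 7 | +1, not an event | +2, event | +3, event |

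From baselines 0 to 2, all three count. What is lost is the subject with baseline 5 who peaks at exactly 6.

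**3. Role of FEV1.** The rule in SAP 6.1 uses the Ordinal Scale only. A subject with FEV1 below 70% of predicted on Day 1 and a score of 4 or less who is intubated is still an event.

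**4. Size per subject, 50 per arm.**

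- Misclassified (event counted as non-event): 1/50 = 2 percentage points.
- Dropped before dosing, assuming 10 events in 50 (20.0%): losing a non-event gives 10/49 = 20.4% (+0.4 points); losing an event gives 9/49 = 18.4% (−1.6 points). The denominator falls too, so the shift is smaller than 2 points here.

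**5. What one event can do to the test (illustrative counts).** Two-sided Fisher's exact p, 50 per arm: 2 vs 10 events gives p = 0.028 and 2 vs 9 gives p = 0.051; 1 vs 8 gives p = 0.031 and 1 vs 7 gives p = 0.059. One lost event can move a result across 5%.

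**6. Effect on power (illustrative rates).** Assume k of 50 subjects per arm have baseline 5, carry the same event rate as the others, and lose all their events. The calculation is a normal approximation at two-sided 5% with n = 50 per arm, not Fisher's test, and each rate p becomes p(1 − k/50).

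| Assumed rates | k = 0 | k = 1 | k = 3 | k = 5 |
|---|---|---|---|---|
| 20% vs 10% | 28.6% | 28.0% | 26.9% | 25.8% |
| 30% vs 10% | 71.1% | 70.0% | 67.7% | 65.3% |
| 40% vs 20% | 59.0% | 57.8% | 55.2% | 52.7% |

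One such subject per arm costs about 0.6 to 1.2 points of power. The loss would be smaller where some of these subjects reach 7 or 8, and larger if they worsen more often than the rest.

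**The case against.** **The inclusions are undated, so they may apply on Day 1.** A reader might infer from exclusion 2 and the schedule that no eligibility criterion reaches Day 1. The documents do not support that. Inclusions 3, 4 and 6 must be met and carry no time point, the objective speaks of enrollment, exclusion 5 (investigator's opinion) is also undated, and the Screening window itself extends to Day 1. This stands: the defect is an unclear time point and an unstated re-check, not an absent criterion. It does not dispose of the matter. A subject who fails on Day 1 under that reading is already randomized and, if not dosed, drops out of the ITT set. Inclusion 4 cannot be re-checked from scheduled data, since oximetry is not repeated.

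**The effect is small and not directional.** The change precedes any drug. Subjects and site staff, apart from the unblinded drug personnel and pharmacists, do not know the assignment (SAP 3.2.2). Losses should therefore be similar in both arms in expectation. The study is exploratory and has no power target. This stands: it limits the severity, and bias towards one arm should not be read into the plan.

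**The analysis set is openly defined.** Both documents say that ITT means randomized and dosed, and SAP 5.1 tabulates the randomized count beside each analysis set. Pre-dose losses will thus be visible. They will not be analysed, and the present order of steps creates some that need not arise.

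**Conclusion.** The point holds as a matter of timing and of the scoring rule. Randomization may precede the first dose by up to 2 days, no Day 1 re-check is stated, and a dosed subject may have baseline 5, for whom an intubation scored 6 is not a primary event. Scores 7 and 8 still count.

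Its size per subject is 2 percentage points of an arm of 50 when misclassified, and less in the worked example of a dropped subject. A reader might carry the 2-point figure over to dropped subjects; the denominators in the working show why that is not generally right. A reader might also infer that FEV1 below 70% on Day 1 distorts the endpoint. It does not: it is an eligibility-timing gap only.

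The total effect is unknown. It needs Screening before Day 1, a move from 4 or less to 5 in the gap, and then either dosing followed by a peak of exactly 6, or no dosing. The documents give no frequency for any of these. The power and Fisher figures rest on assumed rates and counts. The change is worth making because it is cheap, not because a large effect has been shown.

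**What to change.** 1. **Move randomization to Day 1**, after the pre-dose Ordinal Scale and spirometry, in Protocol 7.9, 7.10.1 and Table 1, and in SAP Appendix A. A subject who no longer qualifies is then a screen failure, not a randomized subject lost before dosing.
2. **Use one time point for eligibility.** Reconcile the screening wording of exclusion 2, the enrollment wording of the objective and the undated inclusions 3, 4 and 6, so that the existing criteria refer to the last values before randomization. No threshold changes. As scheduled, the last oximetry value would remain the Screening reading.
3. **State in SAP 6.1 how a baseline above 4 is handled** in the primary analysis, for example by a sensitivity analysis that counts any score of 6 or more as worsening. This is useful even if randomization stays where it is.

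**Cost.** Protocol and SAP wording and one moved cell in each schedule; some waiting on Day 1 while the dose is prepared; a few more screen failures. Adverse event reporting starts at randomization (Protocol 12.2, SAP 7.2), so its start and the Screening entry in the schedule need a matching edit; treatment-emergent events, defined from the start of study drug, are unaffected. Randomization is central and doses are prepared at the site within 4 hours of administration, so the documents show no supply obstacle. The Pharmacy Manual is not available to confirm that.
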